3.4.2 Power for Subgroup Analyses and Other Analyses

Subgroups in Specific Aim 1.

The prespecified subgroup analysis for specific aim 1 is to examine the difference between the methotrexate and mycophenolate mofetil groups within each anatomic location. Using Equation (5), we anticipate having in excess of 80% power to detect a difference of 25% in success rates.

The power for selected secondary outcomes is provided here.

Secondary Outcomes in Specific Aim 1.

1. *Twelve-month endpoint for success.* We assume an additional loss of 5% between 6 and 12 months (that is, in addition to the 10% already lost to follow-up in the first six months). **We expect approximately 78% power to detect a 20% difference in success rates at the 12-month endpoint.**

2. *Time to corticosteroid sparing control of inflammation.* For sample size planning, we use the approximate formula given in Friedman et al (2010) for the number in each group:

$$N = \frac{(Z_\alpha + Z_\beta)^2 (\phi(\lambda_C) + \phi(\lambda_I))}{(\lambda_I - \lambda_C)^2}$$

where λ_C is the hazard in the methotrexate group, λ_I is the hazard in the mycophenolate mofetil group, and $\phi(u) = \frac{u^2}{1 - e^{-uT}}$

where T is the censoring time (6 months). Previous studies suggest a median success time of approximately 3.5 months for mycophenolate mofetil.¹² **Assuming a 10% loss to follow-up, 108 subjects in each group provides 80% power to detect a difference of 2.47 months in the expected difference.** (Note: λ_C is $\log(2)/3.5$ mo. for this calculation.) We assume an alpha of 0.05 (two sided).

3. *Change in BSCVA.* For sample size planning, we assume a T-test comparing change scores between the two drugs, assuming a standard deviation of the change in visual acuity of 6.5 letters.^{13, 14} The sample size of 108 will provide approximately 80% power to detect 2.63 letters of difference in the change score. In other words, **we expect to have 80% power to detect whether mycophenolate mofetil yields 2.63 letters more of improvement than methotrexate, and we will have greater power to detect greater differences.** The power formula is provided in Chow et al and is computationally implemented in R in the function `power.t.test` (which we used).¹⁵

4. *Quality of life.* For a power calculation, we consider the SF-36 questionnaire, which has two scales, the MCS and the PCS. The raw score standard deviation will be assumed to be 8.4 points; we assume a correlation between baseline and six months of 0.6.^{16, 17} Assuming that the baseline score will “explain” roughly 36% of the variance allows us to assume a corrected raw score standard deviation of 6.72 in a simplified calculation in which we treat the analysis as a T-test. The same power calculation formula used in (3) above reveals that **our sample size provides approximately 80% power to detect a raw score difference of roughly 2.57 between the two treatment groups.** This difference is roughly comparable to the small difference in scores found between intermediate uveitis patients and the general population¹⁶, a difference we believe to be more than sufficient to detect clinically significant results. Note that the population mean of this score is standardized to 50 on 0 to 100 scale. Similar analyses will be conducted for the vision related quality of life (i.e. NEI-VFQ-25 and the IND-VFQ).

5. *Rate of discontinuation.* Based on retrospective studies, we expect approximately 13% to discontinue methotrexate due to tolerability and 5% to discontinue due to safety (laboratory abnormalities or other serious adverse events). We expect approximately 4% to discontinue mycophenolate mofetil due to tolerability and 5% to discontinue due to safety.^{12, 18-20} For the purpose of the power calculation, we assume 10% loss to follow-up and consider only the comparison of discontinuation due to tolerability. **We use the power formula given in Freedman et al (p. 104) to calculate a power of 61% for this comparison.**³

6. *Macular edema.* Previous studies suggest approximately 38% of individuals with uveitis will manifest macular edema.²¹ **We have approximately 80% power to detect a difference of a factor of two in the final proportion of macular edema (19% vs 38%).**

7. *Macular thickness.* **A sample size of 108 (before loss to follow-up) provides approximately 80% power to detect a 65 micron difference between the two treatment groups, assuming a standard deviation of 160 microns in the final macular thickness.**²² This analysis is quite conservative, since a difference of 100 microns between these two groups is consistent with previous studies. Moreover, adjustment for variance explained by the baseline thickness (i.e. the use of a smaller effective standard deviation) would yield a still higher effective power.^{22, 23}

Specific Aim 2.

In the primary comparison of Specific Aim 2, we will estimate the effectiveness of rescue therapy, controlling for treatment group and reason for failure.

The primary analysis is (a) to estimate the probability of success on mycophenolate mofetil following failure of methotrexate, with 95% confidence intervals, and (b) to estimate the probability of success on methotrexate following failure of mycophenolate mofetil, with 95% confidence intervals.

These results will also be reported by reason for failure of the first drug, by categories of (i) failure because of inability to tolerate the first drug, (ii) failure of the first drug to achieve control (efficacy), or (iii) failure due to safety.

One analysis of interest is to compare the success rates in these two groups, and we include the sample size considerations for this analysis below. For two drugs (mycophenolate mofetil and methotrexate), we conduct the sample size planning as follows (denoting two drugs simply as A and B). For treatment group $j=0,1$ (0 coding drug B rescue in patients failing drug A therapy, 1 coding drug A rescue in patients failing drug B therapy), we expect $n_j = N_0 r_1 (1 - s_j) r_2$ subjects to be available for Specific Aim 2 (where N_0 is the number of subjects randomized to each treatment, r_1 is the retention fraction in Specific Aim 1 (not lost to follow-up in Specific Aim 1), s_j is the expected success fraction for patients for initial treatment j , and r_2 is the retention fraction in Specific Aim 2).

Thus, the number of available patients for Specific Aim 2 are highly dependent on the results from Specific Aim 1. Scientifically, the result of rescue therapy is important regardless of the result in Aim 1. More power will be available for the primary comparison in Specific Aim 2 if treatment in Specific Aim 1 yielded relatively high and similar failure rates for both drugs. However, even if success rates are very different in Aim 1, the descriptive analyses will still provide important information to guide decision-making on second-line treatment.

Here, $N_0=108$, and r_1 is assumed to be 0.9 (10% loss to follow-up). For planning Specific Aim 2, we assume a success rate of 60% for patients treated with drug A Specific Aim 1, and a success rate of 40% for those treated with drug B. This is a conservative estimate of the difference expected based on retrospective studies^{12, 18-20} and consistent with the pilot study. Finally, we are assuming an additional 5% loss to follow-up during Specific Aim 2 (in addition to the 10% already lost), so that $r_2=0.95$. The results are summarized in the following table, where the number enrolling does not include loss to follow-up, and the “expected complete” column has taken loss to follow-up into account (n_{jk}).

We anticipate the following:

Initial/Second Treatment	Expected Enrollment SA/2	Expected to Complete SA/2
B/A	58.3	55.4
A/B	38.9	36.9

Thus, we expect a total of $n_1=58$ patients (rounding down) to have failed one first-line therapy to be enrolled in rescue therapy. Similarly, we expect $n_0=38$ patients to be enrolled in the other rescue regimen.

Previous observational studies suggest a 42% success rate of mycophenolate mofetil in methotrexate-failing patients.²⁴ A simple power analysis for comparing these proportions may be found from the formula (see Chao et al, p. 87):¹⁵

$$1 - \beta = \Phi \left(\frac{|p_1 - p_0|}{\sqrt{\frac{p_0(1-p_0)}{n_0} + \frac{p_1(1-p_1)}{n_1}}} - z_{\alpha/2} \right)$$

where p_0 is the probability of success with methotrexate rescue following mycophenolate mofetil failure, p_1 the probability of success with mycophenolate mofetil rescue following methotrexate failure, and Φ is the cumulative distribution function of the standard normal distribution. These assumptions yield a power of 0.87 if the rate of success with methotrexate rescue is 0.15. We have approximately 80% power to detect a difference of 17% if the probability of success with mycophenolate mofetil is 0.42.

A power table for sensitivity analysis is provided. We chose selected scenarios of potential interest to show the wide range of scenarios for which we have sufficient power. The main scenario is the first row of the table; in other rows, we varied the number of patients or the success fractions for the first drug used. In particular, the results are not sensitive to the efficacy difference found in Specific Aim 1.

Power Table for Specific Aim 2

Drug A, then Drug B (number)	Drug B, then Drug A (number)	Success probability of Drug B in patients failing Drug A	Success probability of Drug A in patients failing Drug B	Approximate Power
58	38	0.42	0.15	87%
58	38	0.42	0.17	80%
58	38	0.15	0.42	83%
58	76	0.42	0.15	94%
116	38	0.42	0.15	96%
40	40	0.42	0.15	80%
58	38	0.40	0.15	80%

To summarize, the anticipated number of patients from Specific Aim 1 (58 enrolled in Drug A, and 38 in Drug B) should provide approximately 80% power to detect a difference of 25% between the two groups, assuming a success probability of 42% and a two-tailed alpha of 0.05.

Secondary Outcomes in Specific Aim 2.

1. Confidence intervals for the probability of success will be reported for each rescue group and anatomic location (i.e. Patients receiving methotrexate or mycophenolate mofetil as first treatment versus receiving it as their second, rescue treatment). Note that in the event that there are insufficient numbers of patients available in one arm of Specific Aim 2 (for instance, far fewer patients available for methotrexate rescue than we anticipate), confidence intervals for estimating the proportion of success can still be computed for the anatomic locations in the other arm.
2. We propose, for each rescue group, to conduct logistic regression using success as an outcome, and reason for failure of the first drug as a categorical covariate (safety, efficacy, tolerability). An overall likelihood ratio test for each will be conducted, with an alpha of $0.05/2=0.025$.
3. An additional comparison will be undertaken between first-line and rescue patients with both methotrexate and mycophenolate mofetil.
4. Additionally, the same secondary outcomes assessed in Aim 1 will be analyzed using similar methods.

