The primary analysis is a logistic regression with treatment arm as a predictor. For the primary analysis, we propose to use study site as a *random effect* (random intercept model). The null hypothesis is that the regression coefficient for treatment arm equals zero, which will be tested using a likelihood ratio test with one degree of freedom. We will also fit the following models: (a) a model including drug, site, and drug \times site interaction, (b) a model including only drug and site, (c) a model including only drug and country, and (d) a model with drug, country, drug-country interaction, and site within country. Countries or sites with fewer than three observations will be pooled together. Provided there is no evidence of treatment \times site interaction or treatment \times country interaction, we will report pooled treatment effects and confidence intervals. In the event evidence suggests a difference between treatment sites, we will report treatment effects by site, and repeat the analysis excluding particular sites. Similarly, evidence of a treatment \times country interaction will lead us to report treatment effects and confidence intervals by country.

Simulations suggest that use of a model containing interaction terms between site or country and treatment for the primary analysis is undesirable. Such a procedure results in modest loss of power unless the treatment effect is of opposite sign in different sites or countries.

The hypothesis test is to be two-sided with alpha of 0.05. We propose to compute the P-value by permutation testing, based on the block randomization scheme.

Prespecified Subgroup Analysis.

The prespecified subgroup analysis will test the hypothesis that there is a treatment effect separately in each anatomic group, using a logistic regression model.

We denote the two anatomic groups by X_i^3 , which equals 0 when the patient is in the intermediate group and 1 when the patient is in the posterior/pan group. In the intermediate subgroup, we plan to determine whether there is evidence of a treatment effect (regardless of the effect in the posterior/pan group). Specifically, we will conduct this analysis in two ways: anatomical site at enrollment (split into three categories: anterior, anterior/intermediate or intermediate only, and posterior/panuveitis), and anatomical location by history (split into two

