categories: anterior/intermediate or intermediate only, and posterior/panuveitis). Anatomical location by history is considered the prespecified analysis; anatomical location at enrollment will supplement this finding.

We propose to proceed as follows. We propose to begin with Equation (1), adding terms $\beta_3 X_i^3 + \beta_{13} X_i^1 X_i^3$ for anatomic location and for treatment-location interaction. We wish to test the hypothesis that $\beta_{13} = 0$, i.e. that there is a difference in treatment efficacy between the anatomic locations, controlling for country. Alternative models will be fit in which the country, site, and treatment x country terms are omitted.

We will also report relative risks in each substratum, using relative risk regression.

Additional analyses will add gender and age to the predictors. The entire analysis will be repeated for each gender, and separately for each country (US and India) and anatomic location.

Planned Secondary Analyses.

Each of the following secondary analyses is designed to test the hypothesis that treatment assignment affects a given outcome, after controlling for selected covariates. All analyses will be repeated without controlling for covariates (i.e., using treatment assignment as the only predictor). In all cases, appropriate regression diagnostics and/or goodness of fit tests will be performed (further details are given below). In addition, we will compute jackknife influence statistics in each analysis, to determine whether or not any single observation (eyes or patients, as appropriate) have an undue effect on the final conclusion. All models with site effects will be repeated omitting this effect, and again repeated including a treatment-site effect, and with country and/or treatment by country interactions (i.e., pooling within countries when appropriate). When reporting findings, care will be taken to distinguish the single prespecified test from supplemental tests (whether prespecified or unprespecified); exploratory analyses will always be labeled as such. All alpha levels are to be two-sided.

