3.4 Sample Size Evaluation

3.4.1 Primary Calculation

The sample size for the trial will be 216 subjects, which we anticipate will provide approximately 80% power to detect a difference of 20% in the proportion of patients achieving control of inflammation at six months between the methotrexate and mycophenolate mofetil groups.

This sample size was determined based on the primary objective (superiority comparison of mycophenolate mofetil to methotrexate) and primary endpoint (treatment success). We assumed an effect size of 20%, as this was deemed to be clinically meaningful, and well within the distribution of the investigators' prior beliefs from published retrospective studies.

An approximate sample size is provided by the formula

$$2N = \frac{4(Z_{\alpha} + Z_{\beta})^2 \bar{p}(1-\bar{p})}{(p_c - p_i)^2} \quad (5)$$

(see Friedman et al. 2010), where α is the significance level (0.05, two sided), β is one minus the power (the desired power is 80%), p_c is in this case the probability of success in the methotrexate group (we estimate this at 0.4), p_i is the probability of success in the mycophenolate mofetil group (we estimate this at 0.6), and \bar{p} is $\frac{1}{2}(p_i+p_c)$. We assume 10% will be lost to follow-up in the first six months; details are given in the full proposal. This yields approximately 108 patients in each of the two groups, for a total of $2 \times 108 = 216$ subjects.

A power table is provided below as a sensitivity analysis (to show how the detectable effect size changes with varying success rates).

Success rate with Drug A	80% Power		90% Power	
	Detectable effect size	Success rate with Drug B	Detectable effect size	Success rate with Drug B
20%	18%	38%	21%	41%
30%	20%	50%	23%	53%
40%	20%	60%	23%	63%
50%	20%	70%	22%	72%
60%	19%	79%	21%	81%

Simulation confirms that this method yields adequate sample sizes for the logistic regression (results not shown).

Note that for the final analysis, the critical value will be adjusted slightly because of the interim analysis.

Sample size readjustment

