3.7 Multiple comparisons

An alpha of 0.05 will be used for the primary analysis of Specific Aims 1 and the primary analysis of Specific Aim 2. The prespecified subgroup analyses of Specific Aim 1 will be conducted at an alpha level of 0.05 (as stated above) as well. However, the use of an overall test prior to subgroup analysis protects the overall type I error rate for the primary outcome, a procedure we apply within the analysis of each secondary outcome as well.

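### The SAP's claim of more than 80% power for a 25-point difference within each anatomic group fails on its own formula; an even split gives about 69%

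*Combined protocol and SAP*

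**What the plan says.** SAP 3.4.2 (Subgroups in Specific Aim 1) describes the prespecified subgroup analysis as one that will "examine the difference between the methotrexate and mycophenolate mofetil groups within each anatomic location". The next sentence gives its power: "Using Equation (5), we anticipate having in excess of 80% power to detect a difference of 25% in success rates".

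SAP 3.2.2 (Prespecified Subgroup Analysis) confirms the unit of analysis, because the plan is to "test the hypothesis that there is a treatment effect separately in each anatomic group". It names two groups by history: "categories: anterior/intermediate or intermediate only, and posterior/panuveitis). Anatomical location by history is considered the prespecified analysis". SAP 3.7 sets the error rate: "The prespecified subgroup analyses of Specific Aim 1 will be conducted at an alpha level of 0.05".

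The planning inputs are in SAP 3.4.1: Equation (5), two-sided alpha of 0.05, success rates of 0.40 on methotrexate and 0.60 on mycophenolate, and 216 patients. On losses it says "We assume 10% will be lost to follow-up in the first six months". SAP 3.5 makes the complete-case analysis primary, so the evaluable number is the one that counts. No expected subgroup sizes or subgroup-specific success rates are given.

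**The concern.** The whole trial is sized to give about 80% power for a 20-point difference. Raising the difference to 25 points reduces the required number by a factor of about 0.64, since (20/25)² = 0.64. Splitting the trial into two groups reduces the available number by more than that in at least one of them. So a claim of more than 80% power in each group looked wrong on its face.

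The claim bears on how the subgroup results are read. A reader who relies on it would take a non-significant result in one anatomic group as good evidence against a 25-point difference there. At an even split the chance of missing such a difference is about 31%. In the smaller group of a 70/30 split it is about 52%.

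**Working it through.** **Inputs.** Two-sided alpha 0.05 (z = 1.960), 80% power (z = 0.8416), methotrexate rate 0.40, 216 randomized and 10% loss, all from SAP 3.4.1. The 25-point difference is from SAP 3.4.2 and the two groups are from SAP 3.2.2. Evaluable total: 216 × 0.9 = 194.4.

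**Reproducing the primary figure.** Equation (5) is 2N = 4(Zα + Zβ)² p̄(1 − p̄)/d². For 0.40 vs 0.60:

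4 × (1.960 + 0.8416)² × 0.5 × 0.5 / 0.20² = 196.2 evaluable, and 196.2/0.9 = 218.

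This is within 1% of the SAP's 216. The pooled-variance (Fleiss) formula gives 97 per arm, or 108 after 10% loss, which is 216 exactly. The formula and inputs are therefore being read as the SAP uses them.

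**Number needed per subgroup.** For 0.40 vs 0.65, p̄ = 0.525 and d = 0.25:

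4 × (1.960 + 0.8416)² × 0.525 × 0.475 / 0.25² = 125.3 evaluable.

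Two groups need 2 × 125.3 = 250.5 evaluable, or 250.5/0.9 ≈ 278 randomized. The plan has 194 and 216.

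**Power by split.** Inverting Equation (5) for a subgroup with T evaluable patients:

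Power = Φ( d√T / [2√(p̄(1 − p̄))] − 1.960 ).

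At T = 97.2 this is Φ(2.468 − 1.960) = Φ(0.508) = 0.694. The splits below are assumptions.

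| Split of 194.4 evaluable | Larger group | Smaller group |
|---|---|---|
| 50/50 (97.2 each) | 69% | 69% |
| 60/40 (116.6 / 77.8) | 77% | 60% |
| 70/30 (136.1 / 58.3) | 83% | 48% |

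One group reaches 80% only if it holds 125.3/194.4 = 64% of evaluable patients, which leaves the other at about 55%.

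**Other readings, at 0.40 vs 0.65.**

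- Fleiss formula, even split: 70%.
- The unpooled formula that the SAP uses for Specific Aim 2, even split: 72%.
- Even split with no loss to follow-up (108 per group): 74%.
- One-sided alpha of 0.05, even split: 79.5%.
- Whole trial (194 evaluable): 94%. This exceeds 80% but is not a within-group comparison. The SAP does not show how it reached its figure.

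**Other base rates.** The table uses the Drug A range of the SAP's sensitivity table in 3.4.1, with 25 points added.

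| Lower rate | Evaluable needed per group | Power at 97 per group |
|---|---|---|
| 20% | 110 | 75% |
| 30% | 123 | 70% |
| 40% | 125 | 69% |
| 50% | 118 | 72% |
| 60% | 100 | 79% |

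The smallest requirement in this range is 100.2 per group (60% vs 85%). Two groups then need 200.4, still more than 194.4. At an even split, 80% is reached only when the mean of the two arms' rates is at or below about 0.26 or at or above about 0.74. That means a lower rate below about 14% (0.262 − 0.125) or above about 61% (0.738 − 0.125).

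**Detectable difference.** With 97 evaluable per group and a lower rate of 0.40, the difference detectable with 80% power is about 28 points.

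**The case against.** The strongest objection is that the result is conditional. The SAP states no subgroup rates, sizes or losses for this sentence, and it refers the reader to the full proposal for details of the loss assumption. If success rates in the subgroups were well away from 0.40, the claim could be true: 60% vs 85% with no losses gives 83% at an even split. This stands as a condition on the conclusion. It does not rescue the sentence, because the SAP's own plan assumes 10% loss, and with that loss no base rate from 20% to 60% gives both groups 80%.

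A second objection is that SAP 3.2.2 goes on to specify a treatment-by-location interaction term and a test that its coefficient is zero. The figures here do not describe that test, and its power was not computed. The power sentence, however, concerns the within-location comparison, so the interaction test does not support it. The restated figure should say which test it covers.

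Third, the consequence may be limited. The SAP promises to keep the single prespecified test distinct from supplemental ones, to report relative risks within each stratum, and to run an overall test before the subgroup analysis. Elsewhere it reports unfavourable power openly (78% for the 12-month endpoint, 61% for discontinuation). These safeguards make misreading less likely, but they do not correct the number. Low power also does not invalidate a prespecified test, so relabelling the within-group tests as estimation is a matter of preference.

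**Conclusion.** The stated power is wrong as written. At the SAP's planning rate of 0.40 and its 10% loss, a 25-point difference cannot be detected with 80% power in both anatomic groups under any split, and an even split gives about 69% in each. If a common base rate anywhere from 20% to 60% is allowed, even-split power is 69% to 79%. The conclusion rests on three things: the SAP's planning rates apply within subgroups, its loss assumption applies, and the comparison is the simple within-group one. Only the individual power figures depend on the assumed splits; the shortfall of about 56 evaluable patients (250.5 against 194.4) does not. The primary sample size, the primary test and its alpha are unaffected.

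**What to change.** In SAP 3.4.2, state the expected size of each anatomic group and the success rates assumed within it, and name the test that the power refers to. Then replace the claim with the recomputed figure: about 69% for 40% vs 65% at an even split, with a short table for 60/40 and 70/30, or alternatively a detectable difference of about 28 points at 80% power. If the interaction test is meant to be part of the prespecified analysis, give its power separately.

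Presenting the within-group results mainly as estimates with confidence intervals would suit this level of power, but is optional.

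The cost is a few sentences of SAP text and a less favourable stated figure. No patients are added and no analysis changes.

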2.1. Design summary

Study type

- Randomized, observer-masked comparative effectiveness trial
- Block randomization by site: [REDACTED]
- Sample size: 216 patients, 108 patients per arm (Table 1)

Treatment arms

- Oral methotrexate
- Oral mycophenolate mofetil

Treatment timeline

- Phase I
 - Initial treatment from 0-6 months. If treatment success (i.e. achieving corticosteroid-sparing control of inflammation at 6 months), treatment extended to 12 months.
- Phase II
 - Second therapy initiated after failure to achieve corticosteroid-sparing control of inflammation in Phase I (0-6 months).

Outcomes

- **Primary outcome (Specific Aim 1):**
 - Proportion of overall treatment success at 6 months, where treatment success is defined as controlled ocular inflammation (Table 2) with 7.5 mg/day of oral prednisone and ≤ 2 drops/day of topical 1% prednisolone acetate
- **Secondary outcomes**
 - Proportion of corticosteroid-sparing treatment success at 6 months after switching treatments in patients who are a treatment failure in the first 6 months where treatment success is defined as in Aim 1 (**Specific Aim 2**)
 - Time to control of inflammation
 - Time to treatment success
 - Proportion achieving treatment success at 5 months and sustaining, for at least 28 days, to 6 months
 - Proportion achieving treatment success at 12 months in Phase I
 - Phase I treatment success (6-12 months) with complete discontinuation of corticosteroid
 - Proportion achieving treatment success at 6 months in Phase II
 - Change in best spectacle-corrected visual acuity (BSCVA)
 - Presence of macular edema
 - Change in macular thickness
 - Change in vitreous haze as assessed clinically by the Miami (formerly Davis) scale
 - Change in vitreous haze as assessed by fundus photography grading by NEI and Miami (formerly Davis) scales
 - Efficacy for intermediate, posterior and panuveitis subgroups
 - Efficacy for retinal vasculitis
 - Proportion discontinuing due to intolerability
 - Rate of adverse events
 - Proportion discontinuing due to serious adverse events
 - Quality of life (Health related and vision related)

- Dose reduction
- Efficacy of treatment in patients with Vogt-Koyanagi-Harada (VKH) disease
- Proportion of patients beginning with at least 2+ inflammation in anterior chamber cells who experience a 2-step reduction (i.e. decreasing from 2+ to 0.5+; 3+ to 1+; 4+ to 2+).

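### The quality-of-life power figure takes no account of the 10% loss to follow-up: 2.57 points has about 76% power, not 80%

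*Combined protocol and SAP*

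**What the plan says.** SAP section 3.4.2, Secondary Outcomes in Specific Aim 1, item 4 plans the quality-of-life comparison on the SF-36. Its inputs are: "The raw score standard deviation will be assumed to be 8.4 points" and "we assume a correlation between baseline and six months of 0.6". Since the baseline score then explains 36% of the variance, the SAP says this "allows us to assume a corrected raw score standard deviation of 6.72 in a simplified calculation in which we treat the analysis as a T-test". It applies "The same power calculation formula used in (3) above" and concludes that "our sample size provides approximately 80% power to detect a raw score difference of roughly 2.57 between the two treatment groups". Item 4 does not mention loss to follow-up.

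Item 3, on best spectacle-corrected visual acuity, is the calculation referred to. It is a two-sample t-test run with R's `power.t.test` and a standard deviation of 6.5 letters, and it states: "The sample size of 108 will provide approximately 80% power to detect 2.63 letters of difference in the change score".

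The 10% loss over the first six months is set in SAP section 3.4.1 for the primary calculation. In section 3.4.2 it is named in item 2 (time to control) and item 5 (discontinuation). Item 1 (12 months) adds a further 5% to it, and item 7 (macular thickness) marks its 108 as a count taken before loss.

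**The concern.** Items 3 and 4 read alike: same formula, same nominal 108 per arm, no word on attrition. A reader would assume that they rest on the same number of evaluable patients. They do not. The visual acuity figure allows for the 10% loss and the quality-of-life figure does not.

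Two things follow. Under the SAP's own planning assumptions, the power stated for a named secondary outcome is too high. And the power section mixes two sample sizes without saying so, which makes its items hard to compare. Item 4 also sets the 2.57 points against a published difference between intermediate uveitis patients and the general population, so the number is used in an argument.

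**Working it through.** **Inputs**

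- Randomised per arm: 108 (protocol section 2.1; SAP section 3.4.1).
- Loss by six months: 10% (SAP section 3.4.1), so 0.9 × 108 = 97.2 evaluable per arm.
- Adjusted SD: 8.4 × √(1 − 0.6²) = 8.4 × 0.8 = 6.72, which agrees with item 4.
- Test: two-sample t, as in item 3.
- Alpha: 0.05 two-sided. Item 4 does not restate it. The value comes from item 2, and SAP section 3.2.2 makes the secondary tests two-sided.

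**Formula.** Power is the probability that a noncentral t with 2n − 2 degrees of freedom falls outside ± the 97.5% t quantile. The noncentrality is (δ/σ) × √(n/2).

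**Reproducing the plan's figure (n = 108)**

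- Noncentrality: (2.57/6.72) × √54 = 0.3824 × 7.348 = 2.81.
- Power at 2.57 points: 79.9%.
- Difference detectable with 80% power: 2.574 points.
- Sample size needed for 80% power at 2.57 points: 108.3 per arm.

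So the stated 2.57 is the figure with no loss.

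**After the 10% loss (n = 97.2)**

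- Noncentrality: 0.3824 × √48.6 = 0.3824 × 6.971 = 2.67.
- Power at 2.57 points: 75.6% (76.0% by the normal approximation).
- Difference detectable with 80% power: 2.714 points.

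**Could another reading give 2.57 at 97.2 per arm?** None of those tried does. The detectable difference is 2.41 with a one-sided 0.05 test, 3.39 with the unadjusted SD of 8.4, and 3.03 with a change-score SD of 8.4 × √(2 × 0.4) = 7.51.

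**The other Aim 1 figures**

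| Item | SAP states | After 10% loss (97 or 97.2 per arm) | With 108 per arm |
|---|---|---|---|
| Time to control | 2.47 months at 80% | 2.47 (difference in medians) | 2.29 |
| Visual acuity, SD 6.5 | 2.63 letters at 80% | 2.63 | 2.49 |
| Quality of life, SD 6.72 | 2.57 points at 80% | **2.71** | **2.57** |
| Discontinuation, 13% vs 4% | 61% power | 61.5% | 66.2% |
| Macular edema, 19% vs 38% (Fisher) | about 80% power | 80.5% | 84.5% |
| Macular thickness, SD 160 | 65 microns at 80% | 64.6 | 61.3 |

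The 12-month item gives 77.9% at about 92 per arm (108 × 0.85 = 91.8), against a stated 78%. The primary comparison of 0.4 with 0.6 gives 80.1% at 97.2 per arm. Quality of life is the only one of the seven numbered items that matches 108.

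**The case against.** The strongest reply is that item 4 contains no slip in its own terms. It speaks of the trial's sample size, that size is 108 per arm, and 108 with an SD of 6.72 does give 79.9% power. It borrows the formula of item 3, not expressly its evaluable number. Nor is the loss written out for visual acuity or macular edema; there it is inferred from the fact that the numbers reproduce at 97. These points are fair, and they make this an unapplied assumption rather than a faulty sum. They do not give a reason for quality of life alone to be spared the loss.

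A second reply is that the questionnaires are also collected at treatment failure (protocol section 5.1; SAP section 3.2.2, item 5), so attrition might be lower. But visual acuity is also taken at failure, and its figure still uses about 97. The SAP does not make this argument, and partial recovery would not be enough: power at 2.57 points is 78.4% with 104 evaluable per arm and 76.8% with 100.

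A third reply is that the calculation is openly simplified. The planned mixed model also adjusts for age, gender, ethnicity and site, which could raise power by an amount the documents do not give. At 97.2 per arm, a baseline correlation of 0.65 in place of 0.6 would give 79.7%, and a raw SD of about 7.95 in place of 8.4 would give 80%. This stands as a caution: 75.6% depends on the planning inputs. Those inputs are nevertheless the SAP's own, and the claim has to be judged on them. Nor does the word approximately cover the gap, since the same section reports 78% and 61% elsewhere.

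**Conclusion.** The concern holds. Under the SAP's own assumptions (SD 6.72, two-sided 0.05, two-sample t-test, 10% loss by six months), power at 2.57 points is about 76%, some 4 percentage points below the stated figure. The difference detectable with 80% power is about 2.71 points, which is 0.14 points or about 5% larger than stated (2.714/2.574 = 1.054). The conclusion rests on applying the trial-wide 10% loss to quality of life, as the neighbouring figures do.

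The consequence is small. Quality of life is one of many secondary outcomes and did not set the sample size. No test, alpha level or stopping rule depends on this number.

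**What to change.** In SAP section 3.4.2, Aim 1 secondary outcomes, item 4, replace the figure with about 2.71 points at 80% power, or keep 2.57 points and give the power as about 76%. In either case state that this assumes 97 evaluable patients per arm after 10% loss. It would help to add the same statement to items 3 and 6, where the loss is applied but not mentioned. If the sponsor did intend 108 evaluable patients for quality of life, item 4 should say so and give the reason. The cost is one restated number and a short phrase; the design and the analysis do not change.
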